## **12.2 Statistical Analysis Plan**

Descriptive statistics will be used. All data will be summarized by dose cohort, dose expansion and overall subject population. A planned subset analysis on patients who have or have not received previous immunotherapy will be performed. A planned subset analysis based on histologic tumor type will be performed.

## **12.3 Safety**

The adverse events observed will be summarized as frequency, proportion of patients, and exact 95% confidence interval for proportion, categorized by type (organ affected or laboratory determination), severity by CTCAE v4.03 and nadir or maximum values for the laboratory measures), time of onset (i.e. course number), duration, and reversibility or outcome. Tables will be created to summarize these toxicities by dose and course.

## **12.4 Efficacy**

As a secondary endpoint, all responses will be reported using irRECIST and RECIST 1.1 definitions [56]. Because of the potential heterogeneity of the patients, all results will be considered preliminary and hypothesis generating for future studies. Response rate will be summarized by exact binomial confidence intervals. Disease free survival will be summarized with Kaplan-Meier plots to describe the outcome of patients treated on this protocol. The median DFS time will be estimated using standard life table methods.

If a patient is enrolled on the study and is subsequently removed from treatment for any reason prior to the first CT/MRI scan they are not evaluable for treatment efficacy, that patient will not be included in analysis of treatment efficacy specific to response criteria, but will still be included in the general safety analysis with all other patients. Patients who are not evaluable for treatment efficacy will be replaced by additional patient enrollment to ensure a full cohort of evaluable patients.

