**SCHEMA**

- General Enrollment Criteria**
- Advanced refractory solid tumors or lymphoma
  - Age ≥18
  - 14 day treatment washout period
  - At least one candidate treatment lesion (subcutaneous, nodal, or visceral)
    - Accessible for RT
    - Accessible and safe for repeat intralesional injections
  - At least one candidate target lesion, outside of the RT field evaluable for response per irRECIST
  - Adequate hematologic and end organ function
  - No active autoimmune disease
  - Patients with previous checkpoint blockade therapy are eligible

- Concurrent RT (Days 1-5)**
- Cohort 1 (solid tumors): (8 Gy x 3) or (4 Gy x 5)
  - Cohort 2 (lymphoma): (8 Gy x 3) or (4 Gy x 5) or (2 Gy x 2)
- +
- Intralesional SD-101 (Day 1, 8, 15, 22, 29)**  
4 mg injection into RT treatment lesion
- +
- Epacadostat**  
50-300 mg PO bid

Phase I Dose Finding	
3+3 Design: (3-6 patients per dose level, 6-18 patients total)	
Dose level -3:	50 mg PO bid
Dose level -2:	100 mg PO bid
Dose level -1:	200 mg PO bid
Dose level 1:	300 mg PO bid

Phase II Expansion Cohorts	
Simon Two-Stage Design	
Cohort 1:	Solid tumor (16-30 patients) P0=0.05, p1=0.20, r1=1, n1=16, rTot=3, nTot=30, α=0.05, power=0.8
Cohort 2:	Lymphoma (7-14 patients) P0=0.05, p1=0.3, r1=0, n1=7, rTot=2, nTot=14, α=0.05, power=0.8

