**Reporting of Results**

All patients included in the study must be assessed for response to treatment, even if there are major protocol treatment deviations or if they are ineligible. Each patient will be assigned one of the following categories: 1) complete response, 2) partial response, 3) stable disease, 4) progressive disease, 5) early death from malignant disease, 6) early death from toxicity, 7) early death because of other cause, or 8) unknown (not assessable, insufficient data).

All of the patients who met the eligibility criteria should be included in the main analysis of the response rate. Patients in response categories 4-8 should be considered as failing to respond to treatment (disease progression). Thus, an incorrect treatment schedule or drug administration, or failure to complete all prescribed study therapy, does not result in exclusion from the analysis of the response rate. Sub-analyses may then be performed on the basis of a subset of patients, excluding those for whom major protocol deviations have been identified (e.g., early death due to other reasons, early discontinuation of treatment, major protocol violations, etc.). The reasons for excluding patients from the analysis should be clearly reported. There will be a planned analysis of patients who are evaluable for response (see section 12.4) which will be used for the Simon two-stage design.

The 95% confidence intervals should be provided.

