## **12. DATA AND STATISTICAL ANALYSIS PLAN**

### **12.1 Sample Size**

For the dose escalation phase a traditional 3 + 3 design will be used with the goal of determining the MTD through DLT assessment. Per design each cohort will consist of 3-6 patients. The number of patients will depend on the occurrence of DLT (Table 1). We estimate a minimum of 6 patients and a maximum of 18 patients (6 patients/cohort) would be enrolled. Once the MTD is determined patients will be enrolled into either a lymphoma or a solid tumor phase 2 cohort which will generate preliminary efficacy data to determine if the treatment regimen should be considered for a randomized study. Patients treated at the MTD during the phase I will also be used as part of the phase II cohorts to minimize patient numbers. For the solid tumor cohort (cohort 1) we have set a threshold DCR response rate of 20% by irRECIST as worthy of further study and this cohort will enroll 16-30 evaluable patients. In the first stage 16 patients (n1) will be enrolled and greater than 1 response (r1) is required for the trial to proceed. In the second stage an additional 14 patients will be enrolled for a total of 30 patients (nTot) and greater than 3 responses (rTot) are required for the therapy to be deemed worthy of further study in a randomized trial. For the lymphoma cohort (cohort 2) we have set a threshold DCR response rate of 30% by irRECIST as worthy of further study and this cohort will enroll 7-14 evaluable patients. In the first stage 7 patients (n1) will be enrolled and greater than 0 responses (r1) are required for the trial to proceed. In the second stage an additional 7 patients will be enrolled for a total of 14 patients (nTot) and greater than 2 responses (rTot) are required for the therapy to be deemed worthy of further study in a randomized trial. Patients who are not evaluable for treatment efficacy (see section 12.4) will

not be included in the Simon two-stage analysis and will be replaced by additional patient enrollment to ensure a full cohort of evaluable patients.

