The primary endpoint of this study is to determine the MTD of epacadostat when combined with SD-101 and radiotherapy. In the two phase II expansion cohorts we will further assess safety and efficacy of this regimen at the proposed MTD. The expansion will employ a Simon two-stage design to determine if the treatment efficacy warrants further investigation in a randomized study. The sample size was determined by the dose-escalation design combined with a Simon two-stage design for our required efficacy endpoints. When the true response rates are at their respective thresholds both two-stage designs have 80% to reject at the 0.05 level (1-sided) the null hypothesis that the DCR response rate is an unacceptably low 5%. Since patients treated at the MTD will be included in the phase II expansion analysis a maximum of 56 evaluable patients will be enrolled.

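### The planned ordinary exact 95% intervals match neither the level nor the two-stage sampling of the Simon test, so at the pass mark they contain the 5% rate that the test rejects

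*Combined protocol and SAP*

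**What the plan says.** On estimation, section 12.4 says "Response rate will be summarized by exact binomial confidence intervals". Reporting of Results in section 10.1 adds "The 95% confidence intervals should be provided". Neither place mentions the two stages, and neither gives a p-value.

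On testing, section 12.1 sizes both cohorts "to reject at the 0.05 level (1-sided) the null hypothesis", the null being a DCR of 5%. The Schema gives the designs:

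- Solid tumour: "P0=0.05, p1=0.20, r1=1, n1=16, rTot=3, nTot=30, α=0.05, power=0.8"
- Lymphoma: "P0=0.05, p1=0.3, r1=0, n1=7, rTot=2, nTot=14, α=0.05, power=0.8"

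Section 12.1 turns these into count rules. For solid tumours, "greater than 3 responses (rTot) are required for the therapy to be deemed worthy of further study"; for lymphoma, more than 2 of 14 are needed. The smallest passing results are therefore 4/30 and 3/14.

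Section 12.4 also calls the efficacy results preliminary and hypothesis generating. Nothing in the plan says what to conclude if the count rule and the reported interval point different ways.

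**The concern.** The test spends 5% in one tail and takes account of the chance to stop at stage 1. The planned interval spends 2.5% in each tail and treats the final sample as if its size had been fixed. A cohort could then be declared worthy of a randomised trial in a report whose only interval still includes the rate labelled unacceptably low. With nothing pre-specified, the choice of which figure to stress would be made after the data are seen.

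**Working it through.** **Inputs.** From the Schema and section 12.1: solid tumour n1 = 16, r1 = 1, N = 30, r = 3; lymphoma n1 = 7, r1 = 0, N = 14, r = 2; null rate 0.05; target rates 0.20 and 0.30. The 95% level comes from section 10.1. "Exact binomial" is read as Clopper-Pearson, two-sided.

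**1. Reproduce the design.** With X1 ~ Bin(n1, p) and X2 ~ Bin(N − n1, p),

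P(pass | p) = Σ over x > r1 of P(X1 = x) · P(X2 > r − x).

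- Solid tumour at p = 0.05: 0.1463 × 0.1530 + 0.0359 × 0.5123 + 0.0070 = 0.0478. Power at 0.20 is 0.807.
- Lymphoma at p = 0.05: 0.2573 × 0.0444 + 0.0406 × 0.3017 + 0.0038 = 0.0274. Power at 0.30 is 0.810.

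Both agree with the stated 80% power and 0.05 level. These two error rates are also the two-stage p-values at the pass mark.

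**2. Intervals at the pass mark.** The ordinary interval is Clopper-Pearson on s/N. The stage-wise interval orders outcomes by stage and then by total. Its lower limit solves P(continue and total ≥ s | p) = a, and its upper limit solves 1 − P(continue and total ≥ s + 1 | p) = a, where a is 0.025 for 95% and 0.05 for 90%.

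| | Solid tumour, 4/30 (13.3%) | Lymphoma, 3/14 (21.4%) |
|---|---|---|
| One-sided p, stages ignored | 0.061 | 0.030 |
| One-sided p, two-stage | 0.048 | 0.027 |
| Ordinary 95% (planned) | 3.8–30.7%, contains 5% | 4.7–50.8%, contains 5% |
| Stage-wise 95% | 4.1–32.8%, contains 5% | 4.8–51.6%, contains 5% |
| Ordinary 90% | 4.7–28.0%, contains 5% | 6.1–46.6%, excludes 5% |
| Stage-wise 90% | 5.1–29.6%, excludes 5% | 6.3–47.2%, excludes 5% |

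**3. Separate the two causes.** Adjusting for the stages while keeping 95% resolves neither cohort. Moving to 90% without adjusting resolves lymphoma but not solid tumours. Doing both resolves both.

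**4. How often it arises.** One response above the pass mark, the planned 95% interval excludes 5%: the lower limit is 5.6% at 5/30 and 8.4% at 4/14. The conflict is therefore confined to exactly 4/30 and 3/14. Those results have probability 10.0% and 17.6% at the target rates.

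**5. Coverage.** Enumerating all two-stage outcomes, the ordinary 95% interval in the solid-tumour cohort has coverage of 94.0% at a true rate of 31%, where the stage-wise 95% interval has 95.2%. The dip below 95% is confined to a narrow band of rates around 31%. In lymphoma, coverage stays above 95%.

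**6. Bias of the estimate.** Over all outcomes, early stopping pulls the raw rate down, by 1.0 point at 0.20 (solid tumour) and 1.2 points at 0.30 (lymphoma). Among cohorts that pass, the direction reverses: the raw rate is 2.1 and 3.8 points too high on average at those rates. The uniformly minimum variance unbiased estimate (UMVUE) is 3.0 and 4.7 points too high. At the pass mark the UMVUE is 16.0% against 13.3% raw, and 23.7% against 21.4% raw.

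**The case against.** The strongest reply is that no decision depends on the interval. Go or no-go rests on counts, the counts have the stated error rates, and section 12.4 labels the efficacy results preliminary. A two-sided 95% descriptive interval beside a one-sided screening rule is a common convention, and the disagreement touches one count per cohort. All of this stands, and it keeps the point modest. It does not remove it: section 12.1 uses the same DCR count to judge whether a randomised trial is warranted, and the plan does not say that the interval is only descriptive.

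Three stronger readings are tempting, and the figures support none of them.

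- A reader might infer that ignoring the stages is why 5% falls inside the interval. The stage-wise 95% intervals contain 5% too, so the level is the main cause.
- A reader might infer that the planned intervals are too wide. At the same level the stage-wise interval is slightly wider at the pass mark: 28.7 points (32.8 − 4.1) against 26.9 (30.7 − 3.8) in solid tumours at 95%.
- A reader might infer that the rate carried into the next trial is too low, since futility stopping biases it downward. A next trial follows only from a pass, and among passing cohorts the raw rate is too high and the UMVUE higher still.

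**Conclusion.** The concern holds as a mismatch between the planned interval and the planned test, mainly in level and secondarily in sampling. In lymphoma the level explains it entirely; in solid tumours both parts are needed. The consequence is a contradictory report at exactly 4/30 or 3/14, plus a shortfall of about one percentage point in nominal 95% coverage near a true rate of 31% in the solid-tumour cohort. The Simon rule itself is sound and unaffected.

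This rests on four assumptions: exact binomial means Clopper-Pearson; the 95% interval is two-sided; the cohorts finish with exactly 30 and 14 evaluable patients; and the response rate in section 12.4 includes the DCR. Section 12.1 supports the last by calling the Simon endpoint a DCR response rate. If section 12.4 does not cover the DCR, that endpoint has no stated interval method beyond the general 95% line in section 10.1.

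**What to change.** In section 12.4, for the DCR of each Simon cohort:

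- Report the two-stage p-value and a two-sided 90% interval by stage-wise ordering, or the equivalent one-sided 95% lower bound.
- Keep the ordinary exact 95% interval, labelled descriptive.
- State that the Simon count rule decides.

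A bias-corrected estimate such as the UMVUE may be added as a supplement. It should not be offered as a better planning value for the randomised trial.

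The cost is a short edit to the SAP, a few lines of code and one more interval to explain. No extra data are needed, and no decision rule or sample size changes.

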**Table 9: Best Overall Response Evaluation**

Best Overall Response Evaluation		
Target Lesion	New Lesion	Overall Response
CR	No	CR
PR	No	PR
SD	No	SD
PD	Yes or No	PD

Patients with a global deterioration of health status requiring discontinuation of treatment without objective evidence of disease progression at that time should be classified as having “symptomatic deterioration”. Every effort should be made to document the objective progression even after discontinuation of treatment.

In some circumstances it may be difficult to distinguish residual disease from normal tissue.

When the evaluation of complete response depends on this determination, it is recommended that the residual lesion be investigated (fine needle aspirate/biopsy) to confirm the complete response status.

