**Table 10: Study Variables**

Endpoint	Variable	Measurement	Comment
Primary- Phase 1	MTD	CTCAE V4.03	Outlined in section 3. The maximum dose at which <2 of 6 patients experienced a DLT
Primary- Phase 1	DLT	CTCAE V4.03	Outlined in section 3. A DLT is defined as $\geq$ grade 4 injection site reaction OR $\geq$ grade 3 treatment-related non-hematologic toxicity (excluding injection site reactions) OR ORAST/ALT > 3 x ULN with bilirubin > 2 X ULN, OR pneumonitis that requires holding treatment > 14 days. Grade 3 rash will not be included as a DLT if there is no desquamation, no mucosal involvement, if it resolves without systemic corticosteroids by the next scheduled dose of epacadostat or 14 days, whichever is longer, and epacadostat dose intensity is maintained at 75% of planned dose during DLT period (i.e < 8 days of dose interruption). If epacadostat dose intensity cannot be maintained at 75% of planned dose during DLT period as a result of toxicity of any grade this will also be deemed a dose limiting toxicity.
Primary- Phase 2	Safety	CTCAE V4.03	
Primary-Phase 2	DCR (CR+PR+SD)	irRECIST	DCR is the endpoint for the Simon two-stage phase 2 study
Secondary- Phase 2	ARR	irRECIST	Objective response at unirradiated sites, the endpoint for measuring responses
Secondary- Phase 2	Treatment tolerability	CTCAE V4.03	Outlined in section 6.6. DLTs and any other treatment related adverse event requiring discontinuation of ERS therapy will be deemed treatment intolerability. Patients unable to resume epacadostat after 30 days due to toxicity will be labelled as having treatment intolerability. If more than two consecutive doses of SD-101 are missed due to toxicity the patient will be labeled as having treatment intolerability. Patients unable to receive at least 50% of the prescribed radiotherapy dose due to treatment

			toxicity will be labeled as having treatment intolerability.
Correlative	ORR	RECIST and irRECIST	
Correlative	PFS	RECIST and irRECIST	
Correlative	OS	RECIST and irRECIST	
Correlative	PBMC Immunophenotype	FACS	Blood
Correlative	PBMC gene expression	qPCR / Nanostring	Blood
Correlative	Systemic Cytokine Signature	Luminex	Serum
Correlative	Try/Kyn ratio	Mass spectrometry	Serum
Correlative	Tissue Immune Markers	IHC / IF	Tissue
Correlative	Tumor gene expression	qPCR / Nanostring	Tissue
Correlative	Mutational load	Whole exome sequencing/ RNA sequencing	Blood and Tissue
Correlative	T cell receptor diversity	TCR deep sequencing	Blood and Tissue

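### The Simon go/no-go analysis drops and replaces patients removed before the first on-study scan, even for toxicity, deterioration or death, while the main response analysis counts early deaths and unassessable patients as failures

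*Combined protocol and SAP*

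**What the plan says.** Section 12.4 defines the evaluable set by exclusion: if patients are "removed from treatment for any reason prior to the first CT/MRI scan they are not evaluable for treatment efficacy". They stay in the safety analysis. Section 12.1 adds that they will "not be included in the Simon two-stage analysis and will be replaced by additional patient enrollment". The ceiling on accrual is also written for evaluable patients only: "a maximum of 56 evaluable patients will be enrolled".

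Reporting of Results in Section 10.1 takes a different line for the main analysis: "All of the patients who met the eligibility criteria should be included in the main analysis of the response rate". Its categories 4 to 8 (progressive disease, early death from disease, toxicity or another cause, and unknown) all count as failure to respond, and not completing therapy is no ground for exclusion. The same subsection then names a second, "planned analysis of patients who are evaluable for response (see section 12.4) which will be used for the Simon two-stage design".

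Table 10 confirms that "DCR is the endpoint for the Simon two-stage phase 2 study". Under Section 12.1 that result decides whether stage 2 opens and whether the regimen merits a randomized trial. The Study Calendar (Section 9.1) puts imaging at baseline and every 60 days, with visits allowed 7 days either way.

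**The concern.** Being removed before the first on-study scan is unlikely to be unrelated to outcome. If that scan is done on schedule, the interval before it contains radiotherapy, every SD-101 injection (days 1 to 29) and the 30-day DLT period, in patients with refractory disease. Losses in this interval can be toxicity, early death, or what the text under Table 9 describes: "Patients with a global deterioration of health status requiring discontinuation of treatment without objective evidence of disease progression at that time". The evaluability rule treats all of these like a patient who moves away.

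The plan therefore regards early death and unassessability as failure when it reports response, but not when it decides. Patients who were treated and replaced carry no weight in the go rule, and their number is not limited by the accrual ceiling. A regimen that a fair share of patients cannot stay on until the first scan could still be declared worthy of a randomized study.

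**Working it through.** **Inputs.** Schema and Section 12.1: cohort 1 has r1/n1 = 1/16, r/n = 3/30, null 5%, target 20%; cohort 2 has 0/7, 2/14, null 5%, target 30%; one-sided alpha 0.05, power 80%. The share d of treated patients removed before the first on-study scan is not in the documents. Every value of d below is an assumption.

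**Step 1: reproduce the design.** P(go) = sum over x > r1 of Bin(x; n1, p) × P(Bin(n − n1, p) > r − x).

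- Cohort 1: p = 0.05 gives 0.048; p = 0.20 gives 0.807.
- Cohort 2: p = 0.05 gives 0.027; p = 0.30 gives 0.810.

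The stated alpha and power hold for the evaluable population.

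**Step 2: what the smallest go means among treated patients.** Filling n evaluable places takes n/(1 − d) treated patients. If no removed patient has disease control, the smallest go is (r + 1)(1 − d)/n of those treated. At d = 10%:

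- Cohort 1: 30/0.9 = 33.3 treated; 4/33.3 = 12.0%, against 4/30 = 13.3% as counted.
- Cohort 2: 14/0.9 = 15.6 treated; 3/15.6 = 19.3%, against 3/14 = 21.4% as counted.

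**Step 3: false-go if the 5% null is meant for all treated patients.** If removed patients have no disease control, the evaluable DCR is 0.05/(1 − d). If they have half the null rate (2.5%), it is (0.05 − 0.025d)/(1 − d). Putting these into the Step 1 formula gives:

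| d | Cohort 1, none | Cohort 1, half | Cohort 2, none | Cohort 2, half |
|---|---|---|---|---|
| 10% | 0.065 | 0.056 | 0.036 | 0.032 |
| 1/6 | 0.082 | 0.063 | 0.044 | 0.035 |

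With no disease control in removed patients, false-go passes 0.05 once d exceeds about 1.5% in cohort 1 and about 21% in cohort 2. If removed patients have the same DCR as scanned ones, nothing changes.

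**Step 4: if the rates are evaluable rates and the same number is treated.** Take an evaluable DCR of 10% and d = 10%, with removed patients kept as failures. The all-treated rate is 0.10 × 0.9 = 0.09. Keep the cut-offs and treat about the number that the current rule treats:

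- Cohort 1 (1/18, 3/33): P(go) = 0.290, against 0.292 under the current rule.
- Cohort 2 (0/8, 2/16): P(go) = 0.156, against 0.146.

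On this reading the decision barely moves.

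**The case against.** The case for the plan is substantial. The evaluable rule is disclosed and stated consistently in three places, and Section 12.1 sizes both cohorts in evaluable patients, so 5%, 20% and 30% are most naturally evaluable rates. Early losses are not hidden. Safety is the phase II primary objective, tolerability counts toxicity discontinuations (Section 6.7), premature discontinuations are tabulated (Section 12.5), and the main response analysis keeps eligible patients. Section 12.4 calls the efficacy results preliminary. A required life expectancy of at least 6 months should limit early deaths.

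Much of this stands, and it rules out several stronger readings.

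- A reader might infer that the stated alpha is breached. It is not: the Step 3 figures test an all-treated null that the protocol does not state.
- A reader might compare 30 evaluable with 30 treated patients at a 10% evaluable DCR and d = 10%, and read the difference (0.292 against 0.232 at p = 0.09) as the effect of the exclusion. Most of it comes from treating fewer patients, as Step 4 shows.
- A reader might infer a fixed cut-off just before day 53 (60 − 7). The rule turns on the first scan actually done, so an earlier unscheduled scan makes the patient evaluable.
- Death is not named in Section 12.4 or in the Section 8 stopping list. It falls under the rule only through the unrestricted wording about reasons.

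What the objection does not answer is that none of these other summaries enters the go rule, and no Simon result that retains these patients is planned. Calling the results preliminary does not alter a formal rule that opens stage 2 and supports a randomized trial.

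**Conclusion.** The concern holds as a choice of analysis set, not as an error of calculation. As written, informative early losses leave the Simon decision and are replaced, contrary to the principle that the plan applies in its main response analysis. The go/no-go DCR is too high as a description of treated patients whenever removed patients do worse than scanned ones.

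The size is unknown, because it depends on a removal rate that the documents do not give, on the disease control of removed patients, and on which population the 5% null describes. At 10% removal the illustrations are modest. False-go exceeds 0.05 in cohort 1 only, and only if the null is an all-treated rate. If the rates are evaluable rates and the number treated is held about constant, the probability of a go is almost unchanged. The change is worth making because it removes a foreseeable source of bias and brings the decision into line with Section 10.1, not because the present design fails on its own terms.

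**What to change.** Amend Sections 12.1 and 12.4 and Reporting of Results in Section 10.1 as follows.

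- An eligible patient who received study treatment and was removed before the first on-study CT/MRI because of treatment-related toxicity, clinical deterioration or death stays in the Simon analysis and is not replaced.
- Such a patient is classified by a follow-up CT/MRI, under the same irRECIST rules as other patients, if one is obtained before new anticancer therapy. Otherwise the patient counts as not having disease control.
- Only patients removed for reasons unrelated to treatment or disease may be replaced, and each is listed with the reason.
- The evaluable-only Simon result is reported as a sensitivity analysis.
- Section 12.1 states which population the 5%, 20% and 30% rates refer to.

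**Cost.** The observed DCR will be slightly lower, and someone must judge and document the reason for each removal in an open-label trial. If the targets are all-treated rates, power is unchanged. If they are evaluable rates and n stays at 30 and 14, power at 10% removal with no disease control in those removed falls to 0.735 in cohort 1 (p = 0.20 × 0.9 = 0.18) and 0.741 in cohort 2 (p = 0.30 × 0.9 = 0.27), and should be restated.

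Power can be restored. If the null is also an evaluable rate (0.05 × 0.9 = 4.5% of treated), the same cut-offs with n1/n of 18/33 give alpha 0.048 and power 0.803, and 8/16 gives 0.030 and 0.818, for about the number that the current rule would treat. If the null is 5% of treated patients, at least 36 are needed in cohort 1 (r1/n1 = 1/28, r/n = 4/36: alpha 0.032, power 0.800) and 15 in cohort 2 (0/9, 2/15: 0.035, 0.802).
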